[name] developed a web-based intervention (mehealth for ADHD) which enables community-based pediatricians to deliver higher quality ADHD care⁴⁴ leading to children with significantly fewer ADHD symptoms. 45 Subsequently, partnerships with the American Academy of Pediatrics and American Board of Pediatrics helped spread use of the portal beyond practices that participated in research and now includes 60,801 patients cared for by 2,153 pediatricians in 886 practices across the US. These practices use the portal as a registry to manage their entire ADHD patient population. With pediatricians continuing to enroll patients on the portal as part of routine clinical care, opportunity exists to leverage this infrastucture to efficiently develop and test new interventions. The proposed research would fill a sizable gap as the current portal is focused exclusively on young school age children with ADHD and medication adherence has not been targeted nor improved. Specifically, while a randomized controlled trial testing the efficacy of the mehealth for ADHD web intervention demonstrated significant effects on children's treatment outcomes, there was not a significant intervention effect on medication adherence (i.e., 59% of days covered by children in the mehealth for ADHD portal group vs. 54% in the control group). 45 Moreover, the portal is devoid of features for adolescents. In focus groups, pediatricians, parents, and adolescents have repeatedly requested such features.

STUDY DESIGN:

We will conduct a pilot, single-arm, open-label trial of the medication experiment feature among 30 adolescents experiencing uncertainty about continued medicine use (see **Figure 2**). Because the medication experiment feature is not clinically relevant for adolescents taking a non-stimulant ADHD medication, they will be excluded. At the time of enrollment, families will complete baseline measures electronically and schedule an in-person visit. We will verify the medication prescribed and the number of days covered with medicine in the past year using

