All participants will be recruited from Cincinnati Children's Hospital. We will advertise the study to CCHMC employees via flyers and emails to recruit their eligible adolescents to participate. Parents will be able to contact the research team to receive additional information. Those who express interest will complete screening questions needed to verify eligibility criteria. If they are eligible, the research assistant will review the full electronic consent and assent forms with the parent and adolescent via phone call. After we review the content of the consent form with the parent, they will record their consent on REDCap using a study-specific consent form modeled after the eConsent demo on the REDCap Resource Center. We will also explain the study to adolescents (in language appropriate to them; see below), and document their assent in REDCap. Once 30 dyads have been consented and enrolled, parents that filled out the interest form that were never called by the study team will be sent a blind carbon copy email via REDCap that explains that the target participant goal has been met and they will be put on a waitlist in the case of participant attrition. They will also be contacted at study completion to inform them that the study is no longer recruiting.

Inclusion/Exclusion Criteria

Inclusion Criteria: Participants for the study must meet all of the following criteria:

- a. Consent: A parent or legal guardian must provide written informed consent
- b. Assent: Adolescents must provide written assent to participate in the study
- c. Ages 11-15
- d. Treated for ADHD by pediatrician
- e. First prescribed ADHD medicine more than one year prior to enrollment
- f. Filled at least one prescription for a stimulant medication in the past year
- g. Uncertainty about continued ADHD medication use
- h. Only one child per household can participate in the study. For families who have more than one child who is potentially eligible, they may decide which of their children would be the best fit for the study.

Exclusion Criteria: Participants will be excluded from the study if they meet any of the following criteria:

- a. Do not have reliable access to the internet at their home or another location.
- b. Will not permit their child to access the internet for study related activities.
- c. Are not able or willing to send or receive text messages.

Intervention

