At baseline we will collect items from standard UTBC scales⁴⁶ to assess the relevance of pre-intention factors and the strength of their intention to take/give medicine, and items from the validated Adolescent and Parent Medication Barriers Scales^{47, 48} to assess the relevance of

implementation factors (see **Measurement**). Once baseline surveys have been completed, we will create a meHealth account for the dyad and schedule an in-person study visit at the Center for ADHD. Study visits will not be scheduled if there is missing survey data as parent and adolescent engagement providing responses electronically is critical to success of completing the medication experiment which involves tracking outcomes. The study physician will meet with the dyad to gather history and better understand their past experience with medication. The study physician and research assistant will collect the DMIS introductory interview to identify the most recent ADHD medication decision made by family (e.g. stop for summer, resume for school year, adjust dosage, change medication, etc.) and then each will complete the decision making involvement scale independently.

During our development process, we identified the following types of experiments that are often relevant:

- 1. Make no changes. Track current state: continue to take medication as it is currently prescribed.
- 2. Take medication on non-school days. Track effects: If not currently taking medication on non-school days, start taking medication on those days and track the effects.
- 3. Stop taking medication on non-school days. Track effects. If currently taking medication on non-school days, stop taking medication on those days and track the effects.
- 4. Do a formal trial off of medication. Take current medication as currently prescribed for 2 weeks while tracking, then stop taking medication for 2-4 weeks while continuing to track.
- 5. Change dose or change medication. Consider a different medication or different dose of current medication in consultation with study doctor. Track the effects.

The study physician will discuss these options with the dyad, they will then select the medication experiment they would like to complete. Next, the study physician and research assistant will use the meHealth software with the dyad to identify, prioritize, and discuss behavioral targets to monitor during the experiment.

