Subsequently, the adolescent and parent will be asked to independently indicate the option they expect to prefer after the experiment ends (continue [medication regimen from experiment], resume previous medication/dosage, conduct another experiment, return to pediatrician to adjust dosage or change medication, other), their certainty about the decision, and their preferred role in decision-making (see Measures).

The study physician will confirm that there are no cardiac risk factors (adolescent history of heart disease, family history of sudden death in children, hypertrophic cardiomyopathy, long QT syndrome) that might preclude the use of stimulant medications and complete a brief physical exam. The adolescent's pediatrician likely assessed this prior to starting stimulant medication.

All medication experiments involving a change in medication regimen will involve tracking outcomes for 2 weeks on their current regimen and a minimum of 2 weeks after making a change. We will partner with dyads to select the order, typically starting with current regimen. In randomized controlled trials of ADHD medication discontinuation, relapse is typically noticed

within 2 weeks.⁴⁹ Hence, we are confident that most participants won't require repeated cycles of treatment and non-treatment as classically described in the N-of-1 trial literature.⁵⁰ Dyads will be able to reach the study team between visits if untoward effects (e.g. relapse of symptoms/impairment, side effects, etc.) convince them to end the experiment early and/or resume their previous regimen. We will follow best practices for medication experiments recommended in ADHD clinical practice guidelines^{6,7} These include conducting when there are few transitions or demands (i.e. mid school year), and avoiding at beginning of any school year, especially at the start of middle school or high school. The trial on/off medicine is designed to reduce ambivalence about medicine (i.e. document improvement among adolescents who still benefit) which may motivate self-directed changes to support medication continuity.

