At the conclusion of the medication experiment, the research assistant will schedule an inperson study visit at the Center for ADHD. The study physician, adolescent and parents will discuss what was learned using a report generated by mehealth for ADHD to visualize the outcome data that was collected. Subsequently, the adolescent and parent will be asked to independently indicate their preference for what to do next (continue [medication regimen from experiment], resume previous medication/dosage, conduct another experiment, return to pediatrician to adjust dosage or change medication, other), and their preferred role in decision-making. The study physician will then facilitate a discussion to resolve any differences between adolescent and parent preferences and come to a consensus. The parent will receive a study summary document to share with their child's pediatrician so s/he is aware of what was learned and can use this to guide future management decisions. The adolescent and parent will report this decision, their certainty about the decision, their preferred role in decision-making, their involvement in the process of making this decision, and their intentions about taking/giving medicine. We will also ask the parent and adolescent about the usability the medication experiment software (see Measures).

Measurement Strategy: Aggregation of individual trials to estimate a population level treatment effect isn't needed given the strong evidence of stimulant effectiveness among adolescents.¹ Rather, it is important to ascertain whether the use of medication experiments helps adolescents and parents work together to resolve uncertainty about future use of medicine. We will describe the type and number of medication experiments conducted as well as the personal outcomes selected for tracking. We will examine process outcomes like the decision-making involvement, comfort with the decision made, and whether the decision was implemented.

Measures to characterize the sample on demographic, ADHD, and psychosocial factors

- 1. Demographics: Adolescents, parents, and pediatricians will report on age and race/ethnicity. Parents will also report on child insurance status, and their own level of education and mental health history.

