There will be no costs to the subject for participating in this study. The study physician will provide prescriptions, as needed, during trial participation, but participants will be responsible for obtaining ADHD medication from their pharmacy as they do for typical clinical care.

PAYMENT FOR PARTICIPATION

Each parent/adolescent dyad will be compensated \$50 for survey completion and \$100 for completing each study visit. They will additionally receive up to \$100 for time spent submitting data during the medication experiment . This will be pro-rated based on the % of days with complete data reported over days expected. For example, if the medication experiment lasts for 6 weeks and both parent and adolescent entered data for 34 out of the 42 days, they would receive 80.9% of \$100 = \$80.90. Therefore the maximum total compensation throughout the study is \$350.

References

- 5. [name] WB, Sherman SN, Zmitrovich AR, et al. In their own words: adolescent views on ADHD and their evolving role managing medication. Research Support, N.I.H., Extramural Research Support, Non-U.S. Gov't. *Acad Pediatr*. Jan-Feb 2012;12(1):53-61. doi:10.1016/j.acap.2011.10.003
- 6. Pliszka S. Practice parameter for the assessment and treatment of children and adolescents with attention-deficit/hyperactivity disorder. *J Am Acad Child Adolesc Psychiatry*. Jul 2007;46(7):894-921.

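### Drug or dose change in experiment 5: the only described message to the treating pediatrician is a summary the parent receives after the experiment ends (low severity)

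*Combined protocol and SAP*

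**What the plan says.** Inclusion criterion d requires that each adolescent be "Treated for ADHD by pediatrician". In the list of experiments under Intervention, the fifth option reads: "Consider a different medication or different dose of current medication in consultation with study doctor". Cost of Participation says who writes the prescriptions: "The study physician will provide prescriptions, as needed, during trial participation". The same section leaves it to the family to obtain the medication from its usual pharmacy.

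The step that informs the pediatrician appears under Intervention, in the description of the visit held after the experiment: "The parent will receive a study summary document to share with their child's pediatrician". Its stated purpose is that the pediatrician should know the findings and use them in later management. The route applies to all five experiment types.

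Experiments that change the regimen are tracked for 2 weeks on the current regimen and for at least 2 weeks on the changed one. The order is agreed with the dyad and usually starts with the current regimen. Either period can be cut short if the family wishes or if safety requires it.

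**The concern.** The protocol already accepts that the pediatrician should know about the experiment. What is open is when the message goes and who carries it. As described, it goes through the parent after the change has run its course, so it cannot help the pediatrician while the new drug or dose is being taken.

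Potential Risks acknowledges that a different drug or dose may bring side effects. Suppose a family takes such a problem to its usual doctor and does not mention the experiment. That doctor could misjudge the cause, or could renew or adjust the old prescription without knowing of the study's. The participants are aged 11 to 15, so this is a question of patient safety and coordination of care. It has no bearing on the estimates or tests.

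The Background gives some reason not to rely on the parent alone, since it describes organizational difficulties in these families as a barrier to timely refills.

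**Working it through.** The plan states no figure on this point, so the check is a reading of the text plus simple arithmetic on time and counts.

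**1. Could two doctors be prescribing?** Criterion d gives each adolescent a treating pediatrician. Cost of Participation makes the study physician a prescriber during the trial. The protocol does not say whether the pediatrician continues or pauses prescribing in that period. The supportable statement is that there are two *possible* prescribers.

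**2. Is earlier or direct notice described elsewhere?** Four places come close:

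- Measures, Demographics: "Adolescents, parents, and pediatricians will report on age and race/ethnicity". This implies some contact with pediatricians, but it covers demographics only and gives no timing.
- Background, on the portal: pediatric practices use it as a patient registry in routine care. Under Intervention, however, the study opens the account for the dyad, and no link to the treating pediatrician is described.
- Potential Risks, on portal security: identifiable data are stored so that pediatricians can view them. This is a general statement about access and describes no alert about a medication change.
- The decision options, at both visits and in the Decisional Conflict Scale, include going back to the pediatrician for an adjustment. That is a choice about what to do after the experiment.

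Contact during the experiment (Intervention; Symptom & side effect monitoring) runs between the dyad and the study team. Data Safety & Monitoring describes reports to the IRB and the sponsor. None of these amounts to notice of a change in drug or dose.

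**3. How long is the interval?** The inputs are 2 weeks on the current regimen and at least 2 weeks on the changed one (Intervention).

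- Planned experiment length: 2 + 2 = at least 4 weeks.
- Planned time on the changed regimen: at least 2 weeks in either order.
- If the current regimen comes first, which is usual, the pediatrician hears no sooner than 2 weeks after the change, plus the time needed to schedule visit 2.
- If the changed regimen comes first, that delay is 2 + 2 = 4 weeks or more, although the adolescent is back on the earlier regimen for the last 2.
- Payment for Participation uses a 6-week experiment as its example. If that were a regimen change, it would leave 6 − 2 = 4 weeks on the changed regimen. The example does not state the experiment type, so this is only an illustration.
- An experiment that ends early shortens all of these.

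**4. How many dyads?** The sample is 30 dyads and each chooses its own experiment. The protocol gives no expected distribution, so the number choosing experiment 5 lies between 0 and 30.

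**5. Cost of a direct notice:** 30 dyads × 1 letter = 30 letters at most. Fewer are needed if it is sent only for experiment 5.

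**The case against.** The strongest objection is that this argues from silence. Permission to contact a child's own doctor normally sits in the consent and authorization pages. Those pages are not in the available text, and the study-flow figure is not shown. This stands as a limit: the point describes what the available text contains and does not show that the study has made no such arrangement.

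The second objection is that harm needs several steps. The family would have to go past a study team that monitors the experiment and can be reached between visits, and consult the pediatrician without mentioning an experiment it helped to choose. For a double supply, the parent would also have to collect both prescriptions. The study physician takes a history and examines the adolescent before the experiment. All of this stands, and it is why the risk is modest.

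The third is that a parent-carried summary is a real communication route and suits an intervention built on family decisions. That is fair. It does not, however, reach the other doctor while the change is in effect.

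A reader might also infer that the study bypasses the pediatrician from the start. Recruitment is through hospital employees ("We will advertise the study to CCHMC employees via flyers and emails to recruit their eligible adolescents to participate"), current medication is checked from dispensing data, and the pediatrician's cardiac assessment is presumed ("The adolescent's pediatrician likely assessed this prior to starting stimulant medication"). The documents do not support that inference. How families are recruited and how medication is verified say nothing about whether pediatricians are told. The cardiac sentence follows one in which the study physician does the check, so the presumed earlier assessment is additional to it.

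**Conclusion.** The point holds in a limited form. In the available text, when experiment 5 changes the drug or dose, a pediatrician who may still be prescribing is not described as being told until the parent receives a summary at visit 2. The planned time on the changed regimen before then is at least 2 weeks, and shorter if the experiment ends early. Between 0 and 30 dyads could be affected, and the documents give no basis for a narrower figure.

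Severity is low: the safeguards between family and study team are real, and no hypothesis, sample size or analysis is touched. The conclusion rests on two assumptions: that the consent pages and the study-flow figure do not already provide for notice, and that the pediatrician may keep prescribing.

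A reader might go further and conclude that duplicate prescribing is built into the design. The protocol does not say that the pediatrician continues to prescribe, so only the possibility can be stated. Nor does the point carry over with equal force to experiment 4, the trial off medication. There the pediatrician would lack the current regimen, but no new drug or dose is introduced.

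**What to change.** Unless the consent form already provides for it, ask at consent for permission to contact the treating pediatrician. For dyads choosing experiment 5, send a short template notice directly from the study at visit 1. It should state the change in drug or dose, the planned dates, who prescribes during the experiment, and the study contact. Sending it for experiment 4 as well is optional. Families who decline keep the parent-held summary as now planned. If pediatricians are contacted for the demographic items anyway, the notice can go with that contact.

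The cost is one consent line and at most one letter per dyad. Visits, measures and analysis stay as they are.

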dispensing data. During the visit, parents and adolescents will receive training on how to use mehealth for ADHD and will choose one of the five medication experiments to complete together and track the effects for the desired amount of time. Once dyads have completed the medication experiment, they will complete a follow-up study visit to review the results from the experiment, discuss feasibility of the software, and complete end of study measures.

Figure 2.

^{*}Electronic baseline surveys: Demographics, Health-Care Literacy Scale, Vanderbilt Scale/ADHD Self-report, Columbia Impairment Scale, Pittsburgh Side-Effect Rating Scale, Pre-Intention Factors, Medication Barriers, Behavioral Intention, Conflict Behavior Questionnaire, and (adolescents only) Medication Diversion

DURATION:

This IRB protocol covers the phase of the study during which we will test the medication experiment feature developed in collaboration with our stakeholders during the first phase of the study. Families can customize the start and end date as well as the amount of time they track effects in the medication experiment. Thus, families could be enrolled in the study for up to 4-

months. We expect that all 30 dyads will be recruited and complete the study participation over the course of one year.

PROCEDURES:

Research Participant Recruitment and Obtaining Informed Consent

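### Does hypothesis 2 fall short because one mean change in decisional conflict, ending after a facilitated consensus, is not broken down by the options each person recorded?

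*Combined protocol and SAP*

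**What the plan says.** The order of events is in the Intervention section. At visit 1, "The study physician will discuss these options with the dyad, they will then select the medication experiment they would like to complete". After behavioural targets have been set, the adolescent and the parent each "independently indicate the option they expect to prefer after the experiment ends" and rate their certainty. The DCS is not among the electronic baseline surveys in the Figure 2 footnote, which ends with "Behavioral Intention, Conflict Behavior Questionnaire, and (adolescents only) Medication Diversion". The graphic itself is not reproduced in the text available.

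At visit 2, "The study physician, adolescent and parents will discuss what was learned using a report generated by mehealth for ADHD". Each person is then asked to "independently indicate their preference for what to do next", together with a preferred role; no certainty rating is listed at this step. Next, "The study physician will then facilitate a discussion to resolve any differences between adolescent and parent preferences and come to a consensus". Only after that: "The adolescent and parent will report this decision, their certainty about the decision".

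Outcome Measures item 13 names the DCS as the measure of certainty, and its opening question records the option chosen. Under Hypothesis testing, hypothesis 2 expects the within-subject DCS to fall and assigns a paired t-test. Power and Sample Size adds Cohen's d. Disagreement between the independent visit 2 preferences is used in hypothesis 3 (with the Decision-Making Involvement Scale) and hypothesis 5 (with the Conflict Behavior Questionnaire). The decisions made are summarised descriptively.

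**The concern.** Hypothesis 2 carries the uncertainty half of the central hypothesis and is meant to inform a larger trial. Its wording, from pre to post, does not say that the first score is a forecast given after counselling and the second a rating of an agreed decision. A reader could take the result as the effect of the medication experiment alone, when the interval also contains the review of the report and the physician's facilitation.

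A single mean can also conceal different patterns. With 30 respondents of one type and an assumed 20/10 split by whether the person's own preference matched the joint decision, three patterns share a mean fall of 0.5 SD:

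- 0.5 SD in both groups;
- 0 in the 20 and 1.5 SD in the 10: (20×0 + 10×1.5)/30 = 0.5;
- 0.75 SD in the 20 and 0 in the 10: (20×0.75 + 10×0)/30 = 0.5.

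If the gain lay mainly with people who gave up their own preference at the consensus step, the larger trial might want to know. The options are already collected, so leaving them unconnected to the DCS looks like a missed opportunity.

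**Working it through.** **Inputs.** From the protocol: 30 dyads, a paired t-test, a medium effect of d = 0.5, and a retention criterion of 80%, so 0.8×30 = 24 dyads. Assumed: two-sided alpha of 0.05, within-group SD of change set to 1, and the splits. The documents give no SD of DCS change and no expected share of disagreeing dyads. They state no power for hypothesis 2, so there is no plan figure to reproduce.

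**1. Does the interval fit the aim?** The Purpose section attributes the fall in uncertainty to the intervention, and Measurement Strategy asks whether medication experiments help adolescent and parent resolve uncertainty together. The physician's discussion and the consensus belong to that intervention. A score taken after the joint decision is therefore the right endpoint, and a paired t-test on the change estimates what hypothesis 2 describes.

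**2. Could the recorded options show where the change lies?**

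| Point | Option recorded | Certainty listed |
|---|---|---|
| Visit 1, after options discussed and experiment chosen | Expected option, each person | Yes |
| Visit 2, after report, before facilitation | Independent preference | No |
| Visit 2, after consensus | Joint decision | Yes |

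The DCS change spans tracking, report review and consensus for everyone. Splitting people by whether their preference equalled the joint decision shows who changed. It cannot divide the change between steps. The matching group would also pool members of dyads that agreed from the start with members of disagreeing dyads whose view prevailed, and for the latter the consensus step may have mattered most.

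**3. How precise would the groups be?** The half-width of the 95% interval for a group mean change, in SD of change, is t(0.975, n−1)/√n:

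- n = 30: 2.045/5.477 = 0.37
- n = 24: 2.069/4.899 = 0.42
- n = 10: 2.262/3.162 = 0.72
- n = 6: 2.571/2.449 = 1.05

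For a difference between groups of sizes a and b with a+b = 30, it is t(0.975, 28)·√(1/a+1/b), with t = 2.048:

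- 15/15: 2.048×0.3651 = 0.75
- 20/10: 2.048×0.3873 = 0.79
- 24/6: 2.048×0.4564 = 0.93

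Even the best case is wider than the plan's medium effect of 0.5. A balanced split is also unlikely. If one member yields in each disagreeing dyad, mismatches among adolescents and parents together equal the number of disagreeing dyads. Ten mismatches in each table need 20 of 30 dyads to disagree, and fifteen need all 30. Fewer suffice only if both members move.

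**4. Are the three patterns one and the same hypothesis 2 result?** Only the mean is common. The test and Cohen's d divide by the SD of all changes. With within-group SD 1, a 20/10 split and a gap g between group means, the overall SD is √(1 + (2/3)(1/3)g²):

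| Pattern (20 / 10) | g | Overall SD | d | Power, n = 30 |
|---|---|---|---|---|
| 0.5 / 0.5 | 0 | 1.00 | 0.50 | 75% |
| 0 / 1.5 | 1.5 | √1.5 = 1.22 | 0.41 | 58% |
| 0.75 / 0 | 0.75 | √1.125 = 1.06 | 0.47 | 70% |

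Uneven change widens the spread and lowers d, so the planned analysis does respond to it, although d alone does not identify the pattern.

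**The case for a change.** The strongest case for acting is that it costs so little. One sentence would make clear that hypothesis 2 runs from the end of visit 1 counselling to the joint decision. Two small descriptive tables, one for adolescents and one for parents, would use data already held, add no questionnaire and leave the test and its power unchanged. The planners already value visit 2 disagreement enough to build hypotheses 3 and 5 on it. The option coding also has a trap: in the experiment described as "Make no changes. Track current state: continue to take medication as it is currently prescribed", continuing the experiment's regimen and resuming the previous one are the same thing, so agreement could be miscoded.

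Much of this is factually right. The order of events is as described, hypothesis 2 does not repeat it, and no analysis relates the options to the DCS. A report of the result should describe the interval correctly. But the narrative already fixes that interval, and a one-line hypothesis need not restate it. The coding remark is sensible housekeeping for hypotheses 3 and 5, but it does not bear on the validity of hypothesis 2, which uses no option coding. The tables could show only large contrasts between groups formed after baseline, and differences between them would not be causal.

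**Conclusion.** The concern does not hold. Followed as written, the plan gives a valid test of whether decisional conflict falls over the course of the intervention, with an endpoint that suits the stated aim. No bias follows from reporting the overall mean change, and the plan promises no breakdown by intervention component. The proposed breakdown could not deliver one, because certainty is not listed as rated before consensus, and its between-group intervals would have half-widths of about 0.75 to 0.93 SD with 30 respondents of one type. An extra exploratory table is a matter of preference.

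This rests on the narrative order of events, since the Figure 2 graphic is not available. The precision figures rest on assumed splits and are in units of an SD of change that the documents do not give. Whether adolescents and parents are analysed separately is not stated outright; the figures here are for one type of respondent.
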